9.6 Statistical Methods

Statistical testing and inference for immunogenicity and safety analyses are described in Section 9.6.1 and Section 9.6.2, respectively. Unless otherwise stated, all statistical tests will be conducted at the $\alpha=0.05$ (2-sided) level. Section 9.6.3 describes how demographic and baseline characteristics will be summarized.

9.6.1 Statistical Methods for Immunogenicity Analyses

This section describes the statistical methods that address the primary and secondary immunogenicity objectives. Immunogenicity analyses will be conducted for each of the 15 pneumococcal serotypes in V114 separately.

Primary Endpoints/Hypotheses (H1 and H2)

The first primary objective (to compare the serotype-specific OPA GMTs at 30 days postvaccination with V114 versus Prevnar 13TM) will be assessed via the 2 hypotheses.

For each of the 13 shared serotypes, OPA GMTs between participants administered V114 and Prevnar 13TM at 30 days postvaccination will be compared via the following noninferiority hypotheses:

$$\begin{aligned} H_0: \text{GMT}_1/\text{GMT}_2 &\leq 0.50 \text{ versus} \\ H_1: \text{GMT}_1/\text{GMT}_2 &> 0.50 \end{aligned}$$

where GMT_1 is serotype-specific OPA GMT for the V114 group and GMT_2 is serotype-specific OPA GMT for the Prevnar 13TM group. A ratio of 0.50 corresponds to a 2.0-fold decrease of OPA GMT in the V114 group as compared with the Prevnar 13TM group. The same statistical criterion has been previously applied to compare Prevnar 13TM with PNEUMOVAXTM23 for the shared serotypes between these 2 vaccines [Jackson, L. A., et al 2013]. Rejecting the null hypothesis (H_0) at the 1-sided $\alpha=0.025$ level corresponds to the lower bound of the 2-sided 95% CI on the GMT ratio (V114/ Prevnar 13TM) being >0.50 and would lead to the conclusion that the OPA response to V114 for the common serotype is noninferior to that of Prevnar 13TM.

For the 2 serotypes that are unique to V114, OPA GMTs between participants administered V114 and Prevnar 13TM at 30 days postvaccination will be assessed via the following superiority hypotheses:

$$\begin{aligned} H_0: \text{GMT}_1/\text{GMT}_2 &\leq 2.0 \text{ versus} \\ H_1: \text{GMT}_1/\text{GMT}_2 &> 2.0 \end{aligned}$$

where GMT_1 is serotype-specific OPA GMT for the V114 group and GMT_2 is serotype-specific OPA GMT for the Prevnar 13TM group. A ratio of 2 corresponds to a 2.0-fold increase of OPA GMT in the V114 group as compared with the Prevnar 13TM group. The same statistical criterion has been previously applied to compare Prevnar 13TM with PNEUMOVAXTM23 for serotype 6A, which was unique to Prevnar 13TM [Jackson, L. A., et al 2013]. Rejecting the null hypotheses (H_0) at the 1-sided $\alpha=0.025$ level corresponds to the lower bound of the 2-sided 95% CI on the GMT ratio (V114/ Prevnar 13TM) being >2.0 and would lead to the conclusion that the OPA GMT to V114 for the unique serotype is superior to that of Prevnar 13TM.

To address the first primary immunogenicity objectives, the serotype-specific OPA GMTs at 30 days postvaccination will be compared between vaccination groups. Comparisons will be made through the estimation of serotype-specific OPA GMT ratios for each of the 15 serotypes in V114. Estimation of the GMT ratios and 95% CI and the hypothesis test (ie, 1-sided p-value) will be conducted using a cLDA method proposed by Liang and Zeger [Liang, K-Y and Zeger, S. L. 2000] utilizing data from both vaccination groups. In this model, the response vector consists of the log-transformed antibody titers at baseline and 30 days postvaccination. The repeated-measures model will include terms for vaccination group,

time, the interaction of time-by-vaccination group (with a restriction of the same baseline mean across groups), age stratum (ie, 50 to 64 years, 65 to 74 years, and ≥ 75 years) at baseline, and age stratum-by-time interaction. This model will allow for different baseline means for each stratum, but restrict the baseline mean within the age stratum levels to be the same for both vaccination groups. An unstructured covariance matrix will be used to model the correlation among repeated measurements. The Kenward-Roger adjustment will be used with restricted (or residual) maximum likelihood to make proper statistical inference. This model allows the inclusion of participants who are missing either the baseline or postbaseline measurements, thereby increasing efficiency.

Primary Endpoints/Hypotheses (H3)

The second primary objective (proportions of participants with a ≥ 4 -fold rise from prevaccination to 30 days postvaccination for OPA responses for participants administered V114 versus participants administered Prevnar 13TM) will be assessed via the following superiority hypotheses for the 2 serotypes that are unique to V114:

$$\begin{aligned} H_0: p_1 - p_2 &\leq 0.1 \text{ versus} \\ H_1: p_1 - p_2 &> 0.1 \end{aligned}$$

where p_1 is the proportion of participants with a ≥ 4 -fold rise for the V114 group and p_2 is the proportion for the Prevnar 13TM group. A difference of 0.1 corresponds to the V114 group having a 10% higher proportion of participants with a ≥ 4 -fold rise in OPA responses from prevaccination to 30 days postvaccination than the Prevnar 13TM group. Rejecting the null hypotheses (H_0) at the 1-sided $\alpha=0.025$ level corresponds to the lower bound of the 2-sided 95% CI on the difference (V114 - Prevnar 13TM) being >0.1 and would lead to the conclusion that the proportion of participants with a ≥ 4 -fold rise in OPA responses in the V114 group for the unique serotype is superior to that in the Prevnar 13TM group.

To address the second primary immunogenicity objective, the serotype-specific proportion of participants with a ≥ 4 -fold rise will be compared between vaccination groups. Comparisons will be made through the estimation of the difference in the serotype-specific proportion of participants with a ≥ 4 -fold rise for each of the 2 unique serotypes in V114. Estimation of the proportion difference and 95% CI and the hypothesis test (ie, 1-sided p-value) will be conducted using the stratified M&N method (1985), an unconditional, asymptotic method [Miettinen, O. and Nurminen, M. 1985].

Secondary Endpoints/Hypotheses (H4)

The first secondary objective (to compare the serotype 3 OPA GMTs at 30 days postvaccination with V114 versus Prevnar 13TM) will be assessed via the following superiority hypotheses:

$$\begin{aligned} H_0: \text{GMT}_1 / \text{GMT}_2 &\leq 1.2 \text{ versus} \\ H_1: \text{GMT}_1 / \text{GMT}_2 &> 1.2 \end{aligned}$$

where GMT_1 is the serotype 3 OPA GMT for the V114 group and GMT_2 is the serotype 3 OPA GMT for the Prevnar 13TM group. A ratio of 1.2 corresponds to the V114 group having an OPA GMT that is 1.2-fold higher than the OPA GMT in the Prevnar 13TM group.

Rejecting the null hypotheses (H_0) at the 1-sided $\alpha=0.025$ level corresponds to the lower bound of the 2-sided 95% CI on the GMT ratio ($V114/ \text{Prevnar } 13^{\text{TM}}$) being >1.2 and would lead to the conclusion that the serotype 3 OPA GMT in the V114 group is superior to the serotype 3 OPA GMT in the Prevnar 13TM group.

To address the first secondary immunogenicity objective, a cLDA method similar as the one used for the first primary immunogenicity objective (H1 and H2) will be used.

Secondary Endpoints/Hypotheses (H5)

The second secondary objective (proportion of participants with a ≥ 4 -fold rise from prevaccination to 30 days postvaccination for OPA responses for participants administered V114 versus participants administered Prevnar 13TM) will be assessed via the following superiority hypotheses for serotype 3:

$$H_0: p_1 - p_2 \leq 0 \text{ versus}$$

$$H_1: p_1 - p_2 > 0$$

where p_1 is the proportion of participants with a ≥ 4 -fold rise for the V114 group and p_2 is the proportion for the Prevnar 13TM group. A difference of 0 corresponds to no difference in the proportions of participants with a ≥ 4 -fold rise of OPA responses from prevaccination to 30 days postvaccination between V114 and Prevnar 13TM. Rejecting the null hypotheses (H_0) at the 1-sided $\alpha=0.025$ level corresponds to the lower bound of the 2-sided 95% CI on the difference ($V114 - \text{Prevnar } 13^{\text{TM}}$) being >0 and would lead to the conclusion that the proportion of participants with a ≥ 4 -fold rise in serotype 3 OPA responses in the V114 group is superior to that in the Prevnar 13TM group.

To address the second secondary immunogenicity objective, the stratified M&N method used for the second primary immunogenicity objective (H3) will be used.

Other Secondary Endpoints

A similar statistical model as used for the first primary objective will be used to address the secondary objective that evaluates the serotype-specific IgG GMCs at 30 days postvaccination with V114 compared with Prevnar 13TM.

Descriptive statistics with point estimates and within-group 95% CIs will be provided for all other immunogenicity endpoints. For the continuous endpoints, the point estimates will be calculated by exponentiating the estimates of the mean of the natural log values and the within-group CIs will be derived by exponentiating the bounds of the CIs of the mean of the natural log values based on the t-distribution. For the dichotomous endpoints, the within-group CIs will be calculated based on the exact method proposed by Clopper and Pearson [CLOPPER, C. J. and PEARSON, E. S. 1934].

Reverse Cumulative Distribution Curves for both OPA titers and IgG concentrations at 30 days postvaccination with V114 will be graphically displayed by serotype.

A detailed analysis strategy for immunogenicity endpoints is listed in **Table 4**.

Table 4 Analysis Strategy for Immunogenicity Variables

Endpoint/Variable (Description, Time Point)	Primary vs. Supportive Approach [†]	Statistical Method [‡]	Analysis Population	Missing Data Approach
Primary Endpoint				
OPA GMTs at Day 30	P	cLDA [§] (estimate, 95% CI, p-value)	PP	Model-based
	S		FAS	
Proportions of participants with a ≥ 4 -fold rise from prevaccination to 30 days postvaccination for OPA responses for the 2 unique serotypes in V114	P	Stratified M&N (estimate, 95% CI, p-value)	PP	Missing data will not be imputed
	S		FAS	
Secondary Endpoint				
OPA GMTs at Day 30 for serotype 3	P	cLDA [§] (estimate, 95% CI, p-value)	PP	Model-based
Proportions of participants with a ≥ 4 -fold rise from prevaccination to 30 days postvaccination for serotype 3 OPA responses	P	Stratified M&N (estimate, 95% CI, p-value)	PP	Missing data will not be imputed
IgG GMCs at Day 30	P	cLDA [§] (estimate, 95% CI)	PP	Model-based
GMFRs and proportions of participants with a ≥ 4 -fold rise from baseline to 30 days postvaccination for both OPA and IgG responses	P	Descriptive Statistics (estimate, 95% CI)	PP	Missing data will not be imputed

[†] P = Primary approach; S = Supportive approach.
 
[‡] Statistical models are described in further detail below:
 
[§] cLDA model with terms for vaccination group, time, the interaction of time-by-vaccination, age stratum at baseline, and age stratum-by-time interaction.
 
 Stratified analysis using the M&N method [Miettinen, O. and Nurminen, M. 1985] with stratification by the participant's age at the time of randomization (50 to 64 years of age, 65 to 74 years of age, and ≥ 75 years of age).
 
CI = confidence interval; cLDA = constrained longitudinal data analysis; FAS = Full Analysis Set; GMC = geometric mean concentration; GMFR = geometric mean fold rise; GMT = geometric mean titer; IgG = immunoglobulin G; M&N = Miettinen and Nurminen; OPA = opsonophagocytic activity; PP = Per-Protocol.
				

9.6.2 Statistical Methods for Safety Analyses

Safety and tolerability will be assessed by clinical review of all relevant parameters, including AEs and postvaccination temperature measurements.

The analysis of safety results will follow a tiered approach (Table 5). The tiers differ with respect to the analyses that will be performed. AEs (specific terms as well as system organ class [SOC] terms) are either pre-specified as “Tier 1” endpoints or will be classified as belonging to “Tier 2” or “Tier 3” based on the number of events observed.

Tier 1 Events

Safety parameters or AEs of special interest that are identified a priori constitute “Tier 1” safety endpoints that will be subject to inferential testing for statistical significance with p-values and 95% CIs to be provided for between-treatment differences in the proportion of participants with events; these analyses will be performed using the M&N method [Miettinen, O. and Nurminen, M. 1985], an unconditional, asymptotic method. For this protocol, solicited injection-site AEs (redness/erythema, swelling, and tenderness/pain) from Day 1 through Day 5 postvaccination and solicited systemic AEs (muscle pain/myalgia, joint pain/arthritis, headache, and tiredness/fatigue) from Day 1 through Day 14 postvaccination are considered Tier 1 events.

Tier 2 Events

Tier 2 parameters will be assessed via point estimates with 95% CIs provided for differences in the proportion of participants with events (also via the M&N method) [Miettinen, O. and Nurminen, M. 1985].

Membership in Tier 2 requires that at least 4 participants in either treatment group exhibit the event. The threshold of at least 4 events was chosen because the 95% CI for the between-group difference in percent incidence will always include zero when vaccination groups of equal size each have less than 4 events and thus would add little to the interpretation of potentially meaningful differences. Because many 95% CIs for Tier 2 events may be provided without adjustment for multiplicity, the CIs should be regarded as a helpful descriptive measure to be used in review, not a formal method for assessing the statistical significance of the between-group differences in AEs.

In addition to individual events that occur in 4 or more participants in any vaccination group, the broad AE categories consisting of the proportion of participants with any AE, a vaccine-related AE, an SAE, a vaccine-related SAE, and death will be considered Tier 2 endpoints. Nonserious adverse events (NSAEs) will be followed for 14 days postvaccination and SAEs will be followed for 6 months postvaccination. The proportion of participants with maximum temperature measurements meeting the Brighton Collaboration cut points will also be considered Tier 2 endpoints.

Tier 3 Events

Safety endpoints that are not Tier 1 or 2 events are considered Tier 3 events. Only point estimates by treatment group are provided for Tier 3 safety parameters.

Table 5 Analysis Strategy for Safety Parameters

Safety Tier	Safety Endpoint [†]	p-Value [‡]	95% CI for Between-Group Comparison [‡]	Descriptive Statistics
Tier 1	Injection-site redness/erythema (Days 1 to 5)	X	X	X
	Injection-site swelling (Days 1 to 5)	X	X	X
	Injection-site tenderness/pain (Days 1 to 5)	X	X	X
	Muscle pain/myalgia (Days 1 to 14)	X	X	X
	Joint pain/arthralgia (Days 1 to 14)	X	X	X
	Headache (Days 1 to 14)	X	X	X
	Tiredness/fatigue (Days 1 to 14)	X	X	X
Tier 2	Any AE [†]		X	X
	Any Vaccine-Related AE [†]		X	X
	Any SAE [†]		X	X
	Any Vaccine-Related SAE [†]		X	X
	Death [†]		X	X
	Maximum temperature measurements meeting the Brighton Collaboration cut points (Days 1 to 5)		X	X
	Specific AEs by SOC and PT [§] (incidence ≥ 4 of participants in one of the vaccination groups)		X	X
Tier 3	Specific AEs by SOC and PT [§] (incidence < 4 of participants in all of the vaccination groups)			X
[†] These endpoints are broad AE categories. For example, descriptive statistics for the safety endpoint of “Any AE” will provide the number and percentage of participants with at least 1 AE.				
[‡] These analyses will be performed using the M&N method [Miettinen, O. and Nurminen, M. 1985].				
[§] Includes only those endpoints not prespecified as Tier 1 or not already prespecified as Tier 2 endpoints.				
AE = adverse event; CI = confidence interval; M&N = Miettinen and Nurminen; PT = preferred term; SAE = serious adverse event; SOC = system organ class; X = results will be provided.				

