6.3.2 Stratification

Intervention allocation/randomization will be stratified according to the following factors:

- Age at time of randomization
 - Participants 50 to 64 years of age
 - Participants 65 to 74 years of age
 - Participants \geq 75 years of age.

At least 800 participants will be \geq 65 years of age.

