Statistical Methods for Key Immunogenicity Analyses	
Immunogenicity analyses will be conducted for each of the 15 pneumococcal serotypes in V114.
 
For the first primary hypotheses, V114 will be considered noninferior to Prevnar 13™ if the lower bound of the 2-sided 95% CI of the OPA GMTs ratios (V114/Prevnar 13™) for the 13 shared serotypes is greater than 0.50.
 
For the second primary hypotheses, V114 will be considered superior to Prevnar 13™ if the lower bound of the 2-sided 95% CI of the OPA GMTs ratio (V114/Prevnar 13™) for the 2 unique serotypes contained in V114 is greater than 2.0.
 
For these hypotheses, estimation of the serotype-specific OPA GMT ratios and 95% CIs will be calculated using the constrained longitudinal data analysis (cLDA) method [Liang, K-Y and Zeger, S. L. 2000].
 
For the third primary hypotheses, V114 will be considered superior to Prevnar 13™ if the lower bound of the 2-sided 95% CI of the difference (V114 - Prevnar 13™) between proportions of participants with a ≥ 4-fold rise from prevaccination to 30 days postvaccination is greater than 0.1 for the 2 unique serotypes in V114. The between-treatment difference (V114 - Prevnar 13™) and its 95% CI will be calculated using the stratified Miettinen and Nurminen (M&N) method [Miettinen, O. and Nurminen, M. 1985].

Statistical Methods for Key Safety Analyses	
p-Values (Tier 1 endpoints) and 95% CIs (Tier 1 and Tier 2 endpoints) will be provided for between-treatment differences in the percentage of participants with events; these analyses will be performed using the M&N method [Miettinen, O. and Nurminen, M. 1985].

Interim Analyses	
To support the periodic review of safety and tolerability data across the adult V114 Phase 3 program, an external unblinded statistician will provide unblinded interim safety summaries to an independent external DMC for their review. There are no plans to conduct an interim analysis of unblinded immunogenicity data in this study. However, unblinded immunogenicity data will be made available to the DMC upon request to enable a benefit-risk assessment.

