9.8 Multiplicity

The study will have met its primary immunogenicity objectives if noninferiority is demonstrated with respect to the OPA GMTs for the 13 shared serotypes and superiority is demonstrated with respect to both OPA GMTs and the proportions of participants with ≥ 4 -fold rises in OPA responses for the 2 unique serotypes. All hypotheses will be tested individually for each serotype at a 1-sided 0.025 alpha-level. This approach controls the 1-sided type-I error rate at 0.025, and no multiplicity adjustment will be required.

No multiplicity adjustments will be made for the safety comparisons.

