9.10 Subgroup Analyses

To determine whether the intervention effect is consistent across various subgroups, the estimate of the between-group treatment effect (with a nominal 95% CI) will be summarized for the primary immunogenicity endpoint. The 95% CI will only be calculated if there are more than 10 participants in each vaccination group for each subgroup. In addition, a summary of AEs and a summary of solicited AEs will be provided for each subgroup (point estimates only). The following are examples of classification variables:

- Age category (50 to 64 years, 65 to 74 years, and ≥ 75 years)
- Race (eg, White, Black, Asian, and Other)
- Sex (female, male)

Further details of subgroup analyses will be documented in the supplemental Statistical Analysis Plan.

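### The seven Tier 1 solicited-AE tests ignore the age strata used in the randomisation and in H3/H5, giving up a little precision if AE rates differ by age

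*Combined protocol and SAP*

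**What the plan says.** On randomisation, Section 6.3.2 states: "Intervention allocation/randomization will be stratified according to the following factors", and lists one factor, age in three groups (50 to 64, 65 to 74, and 75 or older). At least 800 of the 1200 participants are to be 65 or older; the split between the two older groups is not given.

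For binary immunogenicity endpoints the strata are carried into the analysis. H3 uses stratified M&N. For H5, Section 9.6.1 says that "the stratified M&N method used for the second primary immunogenicity objective (H3) will be used". The Table 4 footnote ("Stratified analysis using the M&N method") identifies the strata as the randomisation age groups.

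For safety the strata do not appear:

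- Section 9.1: "p-Values (Tier 1 endpoints) and 95% CIs (Tier 1 and Tier 2 endpoints) will be provided for between-treatment differences", with M&N named and no stratification.
- Section 9.6.2, Tier 1: tests and intervals for between-arm "differences in the proportion of participants with events; these analyses will be performed using the M&N method". Tier 1 is three injection-site and four systemic solicited AEs, seven in all.
- Table 5 footnote, covering every tier: "These analyses will be performed using the M&N method".

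Section 9.8 adds: "No multiplicity adjustments will be made for the safety comparisons". Section 9.10 reports solicited AEs by subgroup, age included, without intervals.

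**The concern.** The plan distinguishes M&N from stratified M&N, and Section 9.1 names both in adjacent rows. An analyst would therefore read the safety method as unstratified, and the safety section gives no reason for that.

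Stratified randomisation balances the arms within each age group, so differences between age groups contribute almost nothing to the arm difference. An unstratified variance still counts them. When event rates vary with age, the calculated standard error is then larger than the true one.

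In a safety comparison this works in the unhelpful direction: a slightly lower chance of seeing an excess of solicited reactions. These AEs are also primary safety endpoints and the only ones tested formally. What is at stake is precision, not validity. The age subgroup summary does not recover that precision, because it gives no intervals and does not enter the arm comparison.

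**Working it through.** **1. The plan's own safety power.** Table 6 (Section 9.9.2) assumes 600 per arm, two-sided 5% and about 80% power. The check used

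power = Φ{[|p₁ − p₀| − 1.96·√(2p̄(1−p̄)/600)] / √[(p₁(1−p₁) + p₀(1−p₀))/600]}, where p̄ is the mean of p₁ and p₀.

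| V114 / Prevnar 13 (%) | 1.6/0.1 | 5.0/2.0 | 9.1/5.0 | 15.4/10 | 21.2/15 | 26.8/20 | 37.6/30 |
|---|---|---|---|---|---|---|---|
| Power (%) | 80.9 | 80.8 | 79.3 | 80.3 | 79.7 | 79.5 | 79.6 |

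Table 6 reproduces. It is unstratified too, so the safety section agrees with itself.

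**2. Assumptions for the comparison.** From the documents: 600 per arm, 1:1 allocation, three strata, at least 800 of 1200 aged 65 or older. Assumed: 400/500/300 participants from youngest to oldest stratum (n_s = 200/250/150 per arm), arms balanced within strata, weights proportional to stratum size, and the AE rates below.

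**3. Formulas.**

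- Unstratified: V_u = 2p̄(1−p̄)/600, where p̄ is now the overall event rate.
- Stratified: V_s = Σ w_s²·2p_s(1−p_s)/n_s with w_s = n_s/600, which equals 2·Σ n_s p_s(1−p_s)/600².
- Half-width: 1.96·√V. Excess width: √(V_u/V_s) − 1.

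Example, rates 60/50/40%:

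- p̄ = (120 + 125 + 60)/600 = 0.5083
- V_u = 2 × 0.5083 × 0.4917/600 = 0.0008331
- V_s = 2 × (48 + 62.5 + 36)/360000 = 0.0008139
- V_s/V_u = 0.977, so the unstratified interval is √(1/0.977) − 1 = 1.2% wider.

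**4. Results.** Power is evaluated at the difference where the unstratified test has 80% (about 8 points): d = 1.96·√V_u + 0.84·√V_s, and stratified power = Φ(d/√V_s − 1.96). Size was simulated with 400,000 trials per scenario, using two-sided score tests at 5%.

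| Rates by age (%) | V_s/V_u | Half-width, unstratified / stratified (points) | Excess width | Stratified power | Simulated size, unstratified / stratified |
|---|---|---|---|---|---|
| 50/50/50 | 1.000 | 5.66 / 5.66 | 0% | 80.0% | 0.053 / 0.053 |
| 55/50/45 | 0.994 | 5.66 / 5.64 | 0.3% | 80.2% | 0.053 / 0.053 |
| 60/50/40 | 0.977 | 5.66 / 5.59 | 1.2% | 80.6% | 0.051 / 0.051 |
| 65/50/35 | 0.948 | 5.66 / 5.51 | 2.7% | 81.4% | 0.047 / 0.050 |
| 70/50/30 | 0.908 | 5.65 / 5.39 | 5.0% | 82.6% | 0.042 / 0.050 |
| 30/20/12 | 0.972 | 4.64 / 4.57 | 1.4% | 80.8% | 0.046 / 0.050 |

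Conservatism is not visible up to a 20-point gradient around 50%. The 0.053 with no gradient is the same for both tests, so it is not an effect of ignoring strata.

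**5. Other stratum mixes** (400/400/400, 400/600/200, 300/600/300, 200/600/400). At a 30-point gradient the unstratified interval is 2.2% to 3.1% wider and the power gain is 1.2 to 1.7 points. At 40 points the figures are 4.0% to 5.8% and 2.1 to 3.0 points.

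**6. A second check** at the last Table 6 row (control about 30%, difference 7.6 points) with 200 per arm per stratum. Power and size are from 200,000 simulated trials; size is for the unstratified test.

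| Control rates (%) | SE, unstratified / stratified (points) | Power, unstratified / stratified | Unstratified size |
|---|---|---|---|
| 30/30/30 | 2.72 / 2.72 | 79.5% / 79.5% | 0.049 |
| 35/30/25 | 2.72 / 2.71 | 79.5% / 79.8% | 0.048 |
| 40/30/20 | 2.72 / 2.68 | 79.8% / 80.8% | 0.046 |
| 50/30/10 | 2.72 / 2.55 | 80.7% / 84.2% | 0.036 |

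The stratified test stayed between 0.049 and 0.050 throughout.

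**The case against.** The strongest reply is that nothing here is wrong. Plain M&N is valid, and Section 4.2 explains the age strata by weaker OPA responses in participants 75 or older, which is an immunogenicity reason. No document reports an age gradient in solicited AEs. At rates inside the range of Table 6 the effect is tiny: with the strata and formulas above, 35/30/25% gives an interval 0.3% wider, 15/10/5% gives 0.8% (3.46 against 3.43 points, about 0.4 points of power), and 8/5/3% gives 0.4% (2.58 against 2.57).

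All of that stands as a statement of size, and it is why this is an optional improvement. It is not a reason against the change. Section 4.2 explains why randomisation was stratified, not why the safety tests then leave the strata out.

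Other objections carry less weight:

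- *Solicited and other AEs would be analysed differently.* True, but Section 9.6.2 already separates them: Tier 1 is tested, while Tier 2 intervals are declared descriptive and may rest on as few as four events in an arm.
- *A weighted difference may not equal the difference of the displayed percentages.* With arms balanced within strata and size-proportional weights the two coincide; otherwise any gap reflects only the residual imbalance.
- *The stratum weights are not stated, and the Japan-requested analysis in participants 65 or older has only two strata.* Both already apply to stratified M&N for H3, so this change does not create them.
- *Safety is judged mainly by clinical review.* Yes, but the plan still chooses to report seven p-values.

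**Conclusion.** The point holds as a small gain in efficiency and consistency. The seven Tier 1 comparisons are planned without the strata used in the randomisation and in H3 and H5. If solicited AE rates differ by age, their intervals are somewhat too wide and their tests somewhat conservative. For 10- to 20-point gradients the loss is about 0.3% to 1.5% of interval width and 0.2 to 1.0 points of power across the scenarios tried. A 40-point gradient, for which the documents offer no support, costs about 4% to 7% and 2 to 3.5 points. With no gradient nothing is lost.

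Confidence in the reading of the text and in the direction is high. The size depends on assumed age-specific rates and an assumed split of the older strata.

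**What to change.** Make three wording edits:

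1. Section 9.1, key safety analyses: name M&N stratified by the randomisation age groups for the Tier 1 p-values and 95% CIs.
2. Section 9.6.2, Tier 1: the same, with reference to the method used for H3 and H5.
3. Table 5: split the single M&N footnote into stratified M&N for Tier 1 and unstratified M&N for all of Tier 2 (any AE, vaccine-related AE, SAE, vaccine-related SAE, death, temperature and specific terms).

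State the stratum weights once, for H3, H5 and Tier 1 together. In the analysis restricted to participants 65 or older (Section 10.7.1), the strata are the two older groups, as they would be for H3 there.

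No new data are needed, and the stratified M&N program is already required for H3 and H5. If the sponsor prefers the unstratified method, one sentence saying that this is intended, and why, would close the point.
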